Potential AESIs (programmed definition) will be summarized by Interest category and Preferred Term. The interest categories are:

- ‘Embolic and thrombotic events (SMQ)’
- ‘Haematopoietic Thrombocytopenias (SMQ) (broad) or HLT = Thrombocytopenias’.

Potential AESI determined programmatically, related to study vaccine (investigator assessment), will be tabulated similarly.

Those AESI analyses will be presented by phase as well as by time interval. The definition of the different time intervals can be found below.

For potential AESIs determined programmatically, attribution to the intervals will be done similarly to the unsolicited AEs as described in Section 5.1.3 above. For Step 2 of phase allocation of adverse events, the ‘0 - 28 days post-dose’ intervals should be treated similar to ‘active’ periods and the rest as ‘non- active’ periods.

The Definition of the time intervals is shown in the table below. Additionally, in the tables a ‘0-56 days post-dose’ interval and a ‘0-6 months post-dose’ interval should also be shown. The ‘0-56 days post-dose’ interval is the combination of the ‘0 - 28 days post-dose’ interval and the ‘29 - 56 days post-dose’ interval. The ‘0-6 months post-dose’ interval is the combination of the ‘0 - 28 days post-dose’ , ‘29 - 56 days post-dose’ and ‘57 days - 6 months post-dose’ intervals.

Definition of intervals:**SR1004 cohort 1/2**

Dose	Interval	From	to
Post-vaccination 1	0-28 days post dose	Date time of the 1 st vaccination	Min of: 
 • 23:59 at date of last contact (for discontinuations) • 23:59 at date of DB cut-off for interim analyses • Maximum(Date of Vaccination 1 + 28 days at 23:59, date of scheduled visit 4 weeks after 1st vaccination at 23:59)
	29-56 days post dose	One minute after the end of the interval 0-28 days post dose	Min of: 
 • 23:59 at date of last contact (for discontinuations) • 23:59 at date of DB cut-off for interim analyses • One minute prior to date time of vaccination 2
	57 days - 6 months post-dose #	One minute after the end of the interval 29-56 days post dose	Min of: 
 • 23:59 at date of last contact (for discontinuations) • 23:59 at date of DB cut-off for interim analyses

			
 • Date of Vaccination 1 + 183 days at 23:59

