	>6 months post-dose #	One minute after the end of the interval 57 days - 6 months post-dose	Min of: 
 • 23:59 at the date of last contact (for discontinuations) • 23:59 at the date of DB cut-off for interim analyses • 1 minute prior to date time of Vaccination 3 *
Post-vaccination 2	0-28 days post dose	Date time of the 2nd vaccination	Min of: 
 • 23:59 at date of last contact (for discontinuations) • 23:59 at date of DB cut-off for interim analyses • Maximum(Date of Vaccination 2 + 28 days at 23:59, date of scheduled visit 4 weeks after 2nd vaccination at 23:59)
	29-56 days post dose	One minute after the end of the interval 0-28 days post dose	Min of: 
 • 23:59 at date of last contact (for discontinuations) • 23:59 at date of DB cut-off for interim analyses • Date of Vaccination 2 + 56 days at 23:59
	57 days - 6 months post-dose	One minute after the end of the interval 29-56 days post dose	Min of: 
 • 23:59 at date of last contact (for discontinuations) • 23:59 at date of DB cut-off for interim analyses • Date of Vaccination 2 + 183 days at 23:59
	>6 months post-dose	One minute after the end of the interval 57 days - 6 months post-dose	Min of: 
 • 23:59 at the date of last contact (for discontinuations) • 23:59 at the date of DB cut-off for interim analyses • 1 minute prior to date time of Vaccination 3 *
Post-vaccination M12*	0-28 days post dose	Date time of the 3rd vaccination	Min of: 
 • 23:59 at date of last contact (for discontinuations) • 23:59 at date of DB cut-off for interim analyses • Maximum(Date of Vaccination 3 + 28 days at 23:59, scheduled visit 4

			weeks after 3rd vaccination at 23:59)
	29-56 days post dose	One minute after the end of the interval 0-28 days post dose	Min of: 
 • 23:59 at date of last contact (for discontinuations) • 23:59 at date of DB cut-off for interim analyses • Date Vaccination 3 + 56 days at 23:59
	57 days - 6 months post-dose	One minute after the end of the interval 29-56 days post dose	Min of: 
 • 23:59 at date of last contact (for discontinuations) • 23:59 at date of DB cut-off for interim analyses • Maximum(Date of Vaccination 3 + 183 days at 23:59 , day 547 visit at 23:59)

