	>6 months post-dose	One minute after the end of the interval 57 days - 6 months post-dose	Min of: 
 • 23:59 at date of last contact (for discontinuations/completions) • 23:59 at date of DB cut-off for interim analyses

Only for participants who did not receive the 2nd dose, but who received the 3rd one.

* only applicable for cohort 1, and for participant of cohort 2 who have received a 3rd dose

SR1004 cohort 3

Dose	Interval	From	to
Post-vaccination 1	0-28 days post dose	Date time of the 1 st vaccination	Min of: 
 • 23:59 at the date of last contact (for discontinuations) • 23:59 at date of DB cut-off for interim analyses • Maximum(Date of Vaccination 1 + 28 days at 23:59 , date of scheduled visit 4 weeks after 1st vaccination at 23:59)
	29-56 days post dose	One minute after the end of the interval 0-28 days post dose	Min of: 
 • 23:59 at date of last contact (for discontinuations) • 23:59 at date of DB cut-off for interim analyses • Date of Vaccination 1 + 56 days at 23:59

	57 days - 6 months post-dose	One minute after the end of the interval 29-56 days post dose	Min of: 
 • 23:59 at date of last contact (for discontinuations) • 23:59 at date of DB cut-off for interim analyses • Maximum of (Date of Vaccination 1 + 183 days at 23:59 , date of scheduled visit 183 days post 1st vaccination at 23:59)
	>6 months post-dose	One minute after the end of the interval 57 days - 6 months post-dose	Min of: 
 • 23:59 at the date of last contact (for discontinuations) • 23:59 at the date of DB cut-off for interim analyses • 1 min prior to date time of vaccination 2
Post-vaccination M12	0-28 days post dose	Date time of the 2nd vaccination	Min of: 
 • 23:59 at the date of last contact (for discontinuations) • 23:59 at date of DB cut-off for interim analyses • Maximum(Date of Vaccination 2 + 28 days at 23:59 , date of scheduled visit 4 weeks after 2nd vaccination at 23:59)
	29-56 days post dose	One minute after the end of the interval 0-28 days post dose	Min of: 
 • 23:59 at date of last contact (for discontinuations) • 23:59 at date of DB cut-off for interim analyses • Date of Vaccination 2 + 56 days at 23:59

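### SAP AESI intervals, Cohorts 1 and 2: the post-dose 1 row for 29–56 days has no 56-day end when dose 2 is missed, so a late event can be tabulated as an early one

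*SAP*

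**What the plan says.** SAP Section 5.1.3 (AESI Analysis) tabulates potential embolic, thrombotic and thrombocytopenic events in two ways: "Those AESI analyses will be presented by phase as well as by time interval". The intervals come from one table for Cohorts 1 and 2 and another for Cohort 3.

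- **The row at issue.** For Cohorts 1 and 2, the post-vaccination 1 row labelled 29–56 days ends at the minimum of last contact (for discontinuations), database cut-off (for interim analyses) and "One minute prior to date time of vaccination 2".
- **The matching rows.** The post-vaccination 2 row in the same table has "Date of Vaccination 2 + 56 days at 23:59", and the Cohort 3 post-vaccination 1 row has "Date of Vaccination 1 + 56 days at 23:59". The Month 12 rows for Cohorts 1/2 and Cohort 3 and the Month 24 row for Cohort 3 have the same kind of bound. That makes five rows with a fixed 56-day end and one without.
- **The rows that follow.** The 57 days to 6 months row starts one minute after the 29–56 day row ends, and stops at Vaccination 1 + 183 days. It and the >6 months row carry footnote #: "Only for participants who did not receive the 2nd dose, but who received the 3rd one". The Month 12 rows carry footnote *: "only applicable for cohort 1, and for participant of cohort 2 who have received a 3rd dose".
- **The combined intervals.** The 0–56 day "interval is the combination of the" 0–28 and 29–56 day rows. The 0–6 month interval adds the 57 days to 6 months row.

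Protocol Section 10.2 lets a participant who misses a dose receive later ones. It also keeps participants who are stopped from further vaccination under safety follow-up.

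**The concern.** The by-interval table exists to show how soon after a dose these events occur. The SAP foresees a missed dose 2, because footnote # is written for that case, but the row from which the # rows are chained then has nothing to close it at 56 days. Step 1 of the allocation rule in Section 5.1.3 assigns an event by the start and stop of the interval and not by its label. A late event can therefore be placed in an early window, or in two windows at once.

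Participants stopped for a vaccine-related serious event before dose 2 are among those exposed. They receive no further dose, so footnote # gives them no later row.

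No other missed-dose rule closes the row. Protocol Section 9.1.2 imputes a vaccination date for visit timing only, and the footnotes in SAP Section 2.1.2 apply to immunogenicity windows only. SAP Table 1 closes Follow-Up 1 for completers, but it defines phases and not these intervals.

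**Working it through.** **Inputs.** Day 1 is vaccination 1 and dose 2 is planned for Day 57 (SAP Table 1). The interval ends are those in SAP Section 5.1.3. I assume the 4-week visit falls on Day 29 or earlier, so the 0–28 day row ends on Day 29 (1 + 28) and the 29–56 day row starts on Day 30.

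**The label, reproduced.** Vaccination 1 + 56 days is Day 57, and 57 − 30 + 1 = 28 days. With dose 2 given on Day 57, the written rule ends the row one minute before that dose, which agrees with the label.

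**Dose 2 missed.** The third bound drops out. Length = last contact − 30 + 1.

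| Participant | Row covers | Length (days) | Multiple of 28 |
|---|---|---|---|
| Discontinues, last contact Day 85 | Days 30–85 | 85 − 30 + 1 = 56 | 2.0 |
| Discontinues, last contact Day 184 | Days 30–184 | 184 − 30 + 1 = 155 | 5.5 |
| Discontinues, last contact Day 365 | Days 30–365 | 365 − 30 + 1 = 336 | 12.0 |
| Completes, final analysis | none of the three bounds applies | not defined | – |

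**Combined displays for a discontinuer.** The 0–56 day interval should end on Day 57, so any event after that is misplaced in it. The 0–6 month interval should end on Day 184 (1 + 183). Events on Days 58–184 belong there, and that display is wrong only for events after Day 184.

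**Chained row and overlap.** Take a Cohort 1 participant at the final analysis who misses dose 2, receives dose 3 on Day 365 and discontinues with last contact on Day 547.

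- The 29–56 day row covers Days 30–547.
- The 57 days to 6 months row starts on Day 548 and ends on Day 184: 184 − 548 + 1 = −363, so it is empty.
- The >6 months row covers Day 185 to one minute before dose 3 on Day 365.
- An event on Day 200 falls in both 29–56 days and >6 months.
- An event on Day 370 falls in both post-vaccination 1 29–56 days and post-Month 12 0–28 days (Days 365–393).

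Dose 3 in Cohort 1 comes no earlier than about Day 305 (Day 365 minus 2 months). Anyone with # rows who discontinues after dose 3 therefore has a last contact after Day 184, so the empty row is not special to this example.

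**No dose 2 and no dose 3.** Footnote # does not apply, so 29–56 days is the participant's last row.

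**After the fix.** The 29–56 day row is Days 30–57 (28 days), and the 57 days to 6 months row is Days 58–184 (184 − 58 + 1 = 127 days).

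**The case against.** The intended limit is plain from the row's label, from the five matching rows and from the name of the next row, so a programmer would probably apply it. That is fair on intent, but the stop rule as written does not produce it.

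The affected group is narrow. A participant must miss dose 2, stay in follow-up and have a selected event after Day 57. That event will mainly be a serious one, because other adverse events are generally collected for only 28 days after each vaccination (Schedule of Activities, footnote m). The empty row and the overlap also need a third dose, which is planned for Cohort 1 (64 participants) but not for Cohort 2. The intervals were added by SAP Amendment 3 (creation date 09/02/2022), so earlier interim analyses probably did not use them. All of this stands and limits the importance of the point.

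The by-phase tables are unaffected, which also stands. They do not replace the interval table, though: with dose 2 missed, Follow-Up 1 runs to the next vaccination or last contact and does not show timing within that span.

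Four stronger readings are tempting, and the documents do not support them:

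- **The 2-, 5.5- and 12-fold figures as inflated event counts.** They are ratios of window length only.
- **Every event after Day 57 as an error in the 0–6 month display.** Those up to Day 184 are correctly placed there.
- **Completers as shown to be misallocated.** Their row has no stated end; the rule is incomplete, and no particular wrong table follows from it.
- **This row as the only open one that can do harm.** The Cohort 3 post-vaccination 1 >6 months row ends before vaccination 2 and has no vaccination 3 bound. If Month 12 is missed, Month 24 is given and the participant later discontinues, that row overlaps the Month 24 rows.

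**Conclusion.** The rule is wrong as written for a participant in Cohort 1 or 2 who misses dose 2. For those who later discontinue, events after Day 57 enter the 29–56 and 0–56 day displays, and events after Day 184 also wrongly enter 0–6 months. Where dose 3 was given before discontinuation, one event can appear in two intervals. For completers the row has no defined end, and for participants with neither dose 2 nor dose 3 there is no later row.

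The matter is minor. The safety analysis is descriptive, with no formal comparison between groups. The number affected is unknown, because the documents give no missed-dose rate, no discontinuation rate after a missed dose and no AESI rate. The conclusion assumes that the rule is programmed literally and that vaccination 2 means the scheduled second dose, which is how footnote # numbers the doses.

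**What to change.** Make (a) and (b) together, and add (c) for consistency.

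- **(a)** In the Cohorts 1/2 post-vaccination 1 row for 29–56 days, add to the minimum list the bound already used for Cohort 3, "Date of Vaccination 1 + 56 days at 23:59", to apply only if vaccination 2 was not given. Keep the existing vaccination 2 bound for those who received it.
- **(b)** Extend footnote # to every participant who did not receive dose 2. End their >6 months row one minute before vaccination 3 if it was given, and otherwise at last contact for completers as well as discontinuers. The Month 12 >6 months row already does the latter: "23:59 at date of last contact (for discontinuations/completions".
- **(c)** End the Cohort 3 post-vaccination 1 >6 months row one minute before the next vaccination actually received, and otherwise at last contact for discontinuations and completions.

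With (a) alone, a participant with neither dose 2 nor dose 3 would have no row for any event after Day 57.

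The cost is a few lines of SAP text and a small programming change, with no new data. The fix leaves the row longer than its label when dose 2 is given late. Counted from Day 57, the 10-day deferral in protocol Section 10.3 takes it to Day 67, and the 3 weeks in the COVID-19 appendix to Day 78. That is acceptable, because an unconditional 56-day bound would leave a gap before a late dose 2.

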In the initial safety cohort (Cohort 1), RSV preF protein dosing is increased from 50 µg to 150 µg for initial safety assessment. Safety of protein at each dose is assessed before dosing of the Ad26.RSV.preF/RSV preF protein combination or mixture. The dose of the mixture will also be increased from a protein/adeno dose of 50 µg/ 5×10^{10} vp to a protein/adeno dose of 150 µg/ 1×10^{11} vp for initial safety assessment.

In Group 10 of Cohort 1 (Ad26.RSV.preF/RSV preF protein 1×10^{11} vp/150 µg combination given as separate injections in opposite arms on Day 1 and at Month 12), no active boost vaccination will be administered on Day 57 as the combination will not be investigated further for immunogenicity in the regimen selection (Cohort 2).

In the regimen selection cohort (Cohort 2), regimens under consideration include dose ranging with all dose combinations of the mixture, including high dose Ad26.RSV.preF with high dose RSV preF protein; a 2-month prime-boost regimen with a mixture of high dose Ad26.RSV.preF with high dose RSV preF protein; and separate administration (in opposite arms) of high dose Ad26.RSV.preF and high dose RSV preF protein.

In Cohort 2, only Group 17 (Ad26.RSV.preF/RSV preF protein mixture 1×10^{11} vp/150 µg given as a single injection on Day 1 and Day 57) will include an active boost vaccination on Day 57, because it is anticipated that if a Day 57 boost is required it would be the highest dose combination of Ad26.RSV.preF and RSV preF protein.

All Cohort 1 and 3 regimens include a Month 12 booster dose to assess the need for a yearly revaccination. Additionally, the Cohort 3 one-dose regimen includes a Month 24 booster dose to assess the long-term durability of the immune response to the selected dose.

Screening Period

The study includes a maximum 28-day screening period for Cohorts 1 and 2, including but not limited to safety laboratory testing and a 12-lead ECG. As the screening period of participants for Cohorts 1 and 2 will generate sufficient safety data before the start of Cohort 3, screening of

participants for Cohort 3 will be performed on Day 1 without safety laboratory testing and a 12-lead ECG.

Blinding, Control, Study Phase/Periods, Vaccine Groups

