9.1.2. Visit Windows

Visit windows will be allowed as indicated in [Table 12](#), [Table 13](#), [Table 14](#), and [Table 15](#).

The timings of the post-vaccination visits will be determined relative to the actual day of the corresponding vaccination. If a participant misses a vaccination, the post-vaccination visits will be calculated from the imputative vaccination date according to protocol.

Table 12: Visit Windows: Initial Safety Cohort (Cohort 1)

VISIT	Visit Day	Window	Primary Purpose
Visit 2	Day 1	--	FIRST STUDY VACCINATION
Visit 3	Day 8	±2 days	7-day post-first study vaccination safety only visit
Visit 4	Day 15	±2 days	14-day post-first study vaccination safety and immunogenicity visit
Visit 5	Day 29	±3 days	28-day post-first study vaccination safety and immunogenicity visit
Visit 6	Day 57	±3 days	SECOND STUDY VACCINATION
Visit 7	Day 64 (Vac 2 +7 days)	±2 days	7-day post-second study vaccination safety only visit
Visit 8	Day 85 (Vac 2 +28 days)	-3 days/+10 days	28-day post-second study vaccination safety and immunogenicity visit
Visit 9	Day 183 (Vac 1 +26 weeks)	±14 days	26-week post-first study vaccination safety and immunogenicity visit
Visit 10	Day 365	±2 months	THIRD STUDY VACCINATION (MONTH 12 BOOSTER)
Visit 11	Day 372 (Vac 3 +7 days)	±2 days	7-day post-third study vaccination safety only visit
Visit 12	Day 393 (Vac 3 +28 days)	±3 days	28-day post-third study vaccination safety and immunogenicity visit
Visit 13	Day 547 (Vac 3 +26 weeks)	±14 days	26-week post-third study vaccination safety and immunogenicity visit
Visit 14	Day 730 (Vac 3 +12 months)	±1 month	FINAL VISIT: 12-month post-third study vaccination safety and immunogenicity visit

Table 13: Visit Windows: Regimen Selection Cohort (Cohort 2)

VISIT	Visit Day	Window	Primary Purpose
Visit 2	Day 1	--	FIRST STUDY VACCINATION
Visit 3	Day 8	±2 days	7-day post-first study vaccination safety only visit
Visit 4	Day 15	±2 days	14-day post-first study vaccination safety and immunogenicity visit
Visit 5	Day 29	±3 days	28-day post-first study vaccination safety and immunogenicity visit
Visit 6	Day 57	±3 days	SECOND STUDY VACCINATION
Visit 7	Day 64 (Vac 2 +7 days)	±2 days	7-day post-second study vaccination safety only visit
Visit 8	Day 85 (Vac 2 +28 days)	-3 days/+10 days	28-day post-second study vaccination safety and immunogenicity visit
Visit 9	Day 183 (Vac 1 +26 weeks)	±14 days	26-week post-first study vaccination safety and immunogenicity visit

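### For one-dose groups in Cohorts 1 and 2, the Day 57 placebo restarts the AESI clock, so the '0-6 months post-dose' row after the active Day 1 dose covers only about 56 of 183 days

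*SAP*

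**What the plan says.** SAP 5.1.3 (AESI Analysis, definition of intervals) presents potential AESIs by phase and by time interval after each vaccination. In the table shared by Cohorts 1 and 2:

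- The Post-vaccination 1 '29-56 days' interval ends "One minute prior to date time of vaccination 2", or earlier at last contact or data cut-off.
- The next two Post-vaccination 1 intervals ('57 days - 6 months' and '>6 months') carry a footnote: "Only for participants who did not receive the 2nd dose, but who received the 3rd one". Where it applies, the first of these closes at "Date of Vaccination 1 + 183 days at 23:59".
- Post-vaccination 2 opens a new '0-28 days' interval at "Date time of the 2nd vaccination". Active and placebo injections are not distinguished.
- The summary '0-6 months' row for a dose joins its 0-28 day interval to its "29 - 56 days post-dose’ and ‘57 days - 6 months post-dose’ intervals".

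Protocol Table 9 gives Groups 11-16 placebo on Day 57, and Protocol 3.2 confirms it: "In Cohort 2, only Group 17" "will include an active boost vaccination on Day 57, because it is anticipated that if a Day 57 boost is required". Protocol Table 13 nevertheless labels the Day 57 visit "SECOND STUDY VACCINATION" for the whole cohort, and Protocol 3.1.1 counts placebo as study vaccination. In Cohort 1, Group 10 has active vaccine on Day 1, placebo on Day 57 and active vaccine again at Month 12 (Protocol Table 8).

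**The concern.** These tables exist to place a small number of thromboembolic and thrombocytopenia events in time after exposure to the vaccine. In the one-dose groups a participant's exposure is the Day 1 injection, yet the clock is reset by an inert one. A reader who takes '0-6 months post-dose' at face value would believe that six months after the active dose had been summarised, when the row stops at about eight weeks. The reader would also see events from the third month after active vaccine under a label that suggests the first four weeks after a dose.

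Two comparisons are affected. Post-vaccination 2 '0-28 days' means time since active vaccine in Group 17 but time since placebo in Groups 11-16. And the Post-vaccination 1 '0-6 months' row does not mean the same thing in Cohort 2 as in Cohort 3.

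**Working it through.** **Inputs**

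- Vaccination 2 is scheduled 56 days after vaccination 1 (Protocol, Schedule of Activities for Cohorts 1 and 2): 57 − 1 = 56. The visit window is ±3 days (Protocol Tables 12 and 13).
- A vaccination may be postponed by up to 10 days for acute illness or fever (Protocol 10.3).
- The nominal six-month limit is 183 days after vaccination 1 (SAP 5.1.3).
- Cohort 2 group sizes (Protocol Table 9) are 24, 42, 42, 42, 42, 36, 36 and 24, which sum to the stated 288.

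**Length of the row.** Without a second vaccination, and where the footnote applies, the three component intervals run to 183 days, as the SAP states. With the Day 57 injection the third component does not exist, so '0-6 months' reduces to '0-28' plus '29-56'. That is exactly the definition of the '0-56 days' row.

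| Day 57 injection given | Days covered | Share of 183 | Days timed from placebo |
|---|---|---|---|
| on schedule | 56 | 31% | 127 |
| −3 / +3 days | 53 / 59 | 29% / 32% | 130 / 124 |
| on schedule or +3 days, plus 10-day delay | 66 / 69 | 36% / 38% | 117 / 114 |

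**Where later events go** (nominal timing, days since the active dose):

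- 56-84: Post-vaccination 2 '0-28 days'
- 85-112: Post-vaccination 2 '29-56 days'
- 113-239: Post-vaccination 2 '57 days - 6 months'

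An event on day 70 is therefore 70 − 56 = 14 days into Post-vaccination 2.

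**Participants affected.** Groups 11-16: 24 + 4 × 42 + 36 = 228 of 288. With Group 10 (n = 8): 236. Assuming no dropout, the row covers 228 × 56 / 365.25 ≈ 35 person-years in Groups 11-16, against 228 × 183 / 365.25 ≈ 114 if it ran the full 183 days.

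**Does another provision repair it?**

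- The sentence closing SAP 2.1.1, which drops the post-dose 2 period for a one-dose regimen, applies after Cohort 2 has been evaluated. It concerns Cohort 3.
- The by-phase AESI tables do not help, because Follow-Up 1 in SAP Table 1 also ends one minute before the next vaccination.
- Reading '2nd dose' as active doses only does not help either. The footnote also requires a third dose, which Protocol Table 9 does not include, and '29-56 days' would still end at vaccination 2.
- In Cohort 3, '29-56 days' ends at a fixed 56 days and an unrestricted interval follows. Barring discontinuation or cut-off, the row there runs to at least 183 days.

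**The case against.** The strongest defence is that timing from each injection is the SAP's uniform convention. SAP Table 1 starts a new period at each dose for all groups, and AESIs are attributed in a similar way. Every Cohort 1/2 group is cut at the same visit, so regimens have comparable follow-up within a row. The rows also match data collection: non-serious unsolicited AEs are collected only for 28 days after each injection, so beyond about Day 85 the issue concerns mainly SAEs and AEs leading to discontinuation. The analysis is descriptive. All of this stands, and it is why the existing rows should be kept.

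A reader might infer that later events are counted against placebo. The documents do not support that. SAP 5 lays the safety tables out by regimen, so a Group 14 event stays in the Group 14 column and nothing moves to Group 18. Only the row changes.

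A reader might also infer that 127 of 183 days (69%) are lost. They are relabelled. The Post-vaccination 2 rows follow on without a gap, so the two '0-56 days' rows together cover about the first 112 days. Only days 113-183 (71 days, 39%) share a row with later time. The SAP also provides for listings by phase and time point, and for listings or narratives of severe and serious events.

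None of this gives the reader a row that states six months after the active dose, and one row carries that label while covering less than a third of it. The full-collection window on days 56-84 is also where the '0-28 days' label is most misleading.

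**Conclusion.** The point holds as a fault of labelling and comparability in the Cohort 1/2 AESI tables. For Groups 11-16, and for Group 10 before Month 12, the Post-vaccination 1 '0-6 months post-dose' row covers about 56 of 183 days (29% to 38% across the permitted timings) and duplicates '0-56 days'. Post-vaccination 2 rows mix time since placebo with time since active vaccine across regimens, and the '0-6 months' row cannot be set beside its Cohort 3 namesake.

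It does not bias comparisons between regimens within a row, and the 0-28 and 29-56 day intervals after the active dose are essentially intact. The figures assume that participants receive the Day 57 injection and remain in follow-up. Describing Day 1 as the only active dose fits Groups 11-16 under the current protocol. It does not fit Group 10.

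**What to change.** Keep the injection-anchored rows. Add one AESI display for Cohorts 1 and 2 in which '0-28', '29-56', '57 days - 6 months', '>6 months' and the combined '0-6 months' intervals run from Day 1 and do not restart at the Day 57 placebo. Apply it to Groups 10-16 and, with the same Day 1 clock, to the all-placebo comparators, Groups 8 and 18. Leaving placebo on the current clock would set 183-day active windows against 56-day placebo windows in one row. If the pooled Cohort 1 placebo column of Protocol 11.2.1 is used, the same clock should apply to all of it.

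For Groups 8 and 10 this clock ends at the Month 12 vaccination. The same should hold for any Cohort 2 participant with a third dose, a case for which the SAP's footnotes allow.

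Add two footnotes: that the existing Post-vaccination 1 '0-6 months' row is truncated at vaccination 2, and that non-serious AEs are collected only for 28 days after each injection. The cost is SAP wording, one derived variable and one extra table. No data collection changes.
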